4.2.1.1 Definition of Primary Estimand

In accordance to the Addendum to International Council on Harmonization (ICH) E9 and to ensure alignment between trial objective, trial design, data collection, analysis, and interpretation, the estimand which describes the target of estimation and its five attributes including population, treatment condition of interest, variable (endpoint), intercurrent events (IECs; defined as events that can occur post-randomization and preclude or affect the interpretation of the variable) and summary of measure are described in Table 4.

Table 4 Attributes for the Estimand of the Primary Endpoint

Attribute	Description
Estimand	The primary endpoint will be evaluated irrespective of taking rescue therapy, treatment discontinuation due to SDCR, as though participants with treatment discontinuation due to NSDCR continued treatment and as though participants with missing data after SDCR, rescue therapy, treatment interruption due to infection continued with placebo.
Population	The population targeted are all participants recruited to the study (satisfying all inclusion criteria) and are part of the mITT restricted to AChR+.
Variable	MG-ADL total score
Treatments	Experimental Treatment: Satralizumab 120 mg (for participants with body weight ≤100 kg) or 180 mg (for participants with body weight >100 kg) and background therapy. Control Treatment: Placebo, administered for 24 weeks and background therapy.
Intercurrent Events	See next Section 4.2.1.2.
Summary of Measure	The difference in the change from baseline to Week 24 in MG-ADL total score. An estimate of the treatment effect will be computed using an analysis of covariance regression approach using the "Variable" as a response and adjusting for randomization stratification factors (background therapy, auto-antibody type, region) and the baseline "Variable" value. The computation will be performed on a completed data set which is obtained by a mixed model repeated measures imputation model.

AChR+=AChR-antibody seropositive (participants/population); MG-ADL=Myasthenia Gravis Activities of Daily Living; mITT=modified intent to treat; NSDCR=not study drug or condition related; SDCR=study drug or condition related.

4.2.1.2 Intercurrent Events for the Primary Estimand

In this section, we will discuss specifically how ICEs are categorized and approaches for handling missing data due to ICEs.

In this study, three different ICEs are considered:

- · Withdrawal from study treatment
- Receiving a rescue therapy
- Treatment interruption due to infection.

As described in Table 5, the ICEs are classified into two main categories:

- Study Drug or Condition Related ICE (SDCR ICE)
- Not Study Drug or Condition Related ICE (NSDCR ICE).

For the generic ICE "Withdrawal from study treatment" information on the cause and categorization into whether the interruption is SDCR or NSDCR is collected in the electronic Case Report Form (eCRF):

- NSDCR: Pregnancy, study terminated by Sponsor
- SDCR: Adverse Event (AE), death, lack of efficacy
- NSDCR or SDCR: Lost to follow-up, protocol deviation, withdrawal by subject, physician decision, other.

The last bullet collects cause that the investigator will be asked for categorization into NSDCR or SDCR in the eCRF.

Depending on to the classification of ICEs, we propose estimand strategies and statistical imputation methodology in handling SDCR- and NSDCR-ICEs in Table 5.

 Table 5
 Handling of ICEs for the Primary Endpoint

Intercurrent Event Classification	Study Drug or Condition Related (SDCR)	Not Study Drug or Condition Related (NSDCR)
Intercurrent event	Withdrawal from study treatment (AE, death, lack of efficacy). ¹ Lost to follow-up, protocol deviation, withdrawal by subject, physician decision and other, that are specified for the individual participant as SDCR. Receiving a rescue therapy. ² Treatment interruption due to infection. ³	Withdrawal from study treatment (Pregnancy, study terminated by Sponsor). Lost to follow-up, protocol deviation, withdrawal by subject, physician decision, other., that are specified as NSDCR for the individual participant.
Estimand Strategy	Treatment Policy In the treatment policy strategy, the occurrence of SDCR ICE is ignored and measurements of the variable of interest are used as such. In other words, the analysis does not make any statistical adjustment for SDCR ICE.	Hypothetical Approach The hypothetical approach envisages a scenario wherein it is presumed that NSDCR ICE would not have occurred. Thus, assumes that NSDCR ICE did not happen in the participants who consented to participate.
Data Collection	Regardless of ICE occurrence, the participant will be ask endpoint and data collection will continue as long as poss	ed to remain in the study to be evaluated for the primary efficacy sible.
Data Strategy	Data are used as available to estimate a treatment effect irrespective of the occurrence of SDCR ICE. This assumption will estimate the treatment effect by analyzing outcomes as they were observed, assuming rescue therapy is part of the standard treatment regimen and hence data are considered as recorded.	All data after an ICE is ignored.

Table 5 Handling of ICEs for the Primary Endpoint

Intercurrent Event Classification	Study Drug or Condition Related (SDCR)	Not Study Drug or Condition Related (NSDCR)
Imputation Strategy	If data are unavailable, or only partial data are available subsequent to a SDCR ICE, then data are used as available and the remainder is imputed using copy reference. Data are imputed using copy reference methodology (i.e., data are imputed from the placebo arm). The underlying assumption being that participants who discontinue the active arm did not get a benefit from the proposed treatment after the SDCR ICE. In other words, the participant profile following SDCR ICE tracks that of the reference arm but starting from the benefit already obtained.	Data are imputed using a missing at random assumption that is data will be imputed conditional on observed data. The imputation under a missing at random assumption estimates a treatment effect as if the ICE had not happened.

¹ For the generic ICE "Withdrawal from study treatment" information on the cause and categorization into whether the interruption is study drug or condition related (SDCR) or not SDCR (NSDCR) is collected in the electronic Case Report Form.

If a participant has recorded multiple ICEs, then the category of the first ICE will determine the handling strategy of all subsequent missing data.

² Receiving rescue therapy might not result in a treatment interruption but is a relevant ICE in this study that always falls under the SDCR category.

 $^{^{\}rm 3}$ Treatment interruption due to infection will always be categorized as SDCR.

The precise statistical imputation methodology is detailed in section on missingness and imputation.

For the efficacy analysis data entries will be mapped to the closest visit available. No visit will be mapped across their respective period for DB or OLE. If two data entries are mapped to the same visit, then the one closer to it and later will be used.

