2.2 SAMPLE SIZE DETERMINATION

Determination of sample size is based on all globally enrolled participants. In this study, approximately 185 participants will be enrolled and randomized in a 1:1 ratio to each treatment group (satralizumab or placebo). Randomization will be stratified by baseline SOC treatment, region, and auto-antibody type as described in the Study Protocol, Section 3.1.

The estimated sample size required to demonstrate efficacy with regard to the MG-ADL is based on the AChR+ population and the following assumptions:

- The primary hypotheses test in the AChR+population is the difference between the placebo and satralizumab groups in the change from baseline to Week 24 in total MG-ADL score
- The assumed change from baseline to Week 24 in the placebo group is 2.3 points
- The assumed change from baseline to Week 24 in the satralizumab group is 4.3 points
- The assumed change from baseline accounts for approximately 10% of participants in the satralizumab group and approximately 20% of participants in the placebo group receiving rescue therapy
- The standard deviation (SD) of the change from baseline to Week 24 is 3.97 in both the placebo and satralizumab groups
- The assumed study treatment withdrawal rate is 10%

The assumptions are based on data reported in Howard et al. (2017). Due to changes in the treatment landscape the assumed mean change from baseline to Week 24 in the satralizumab arm is now assumed to be 4.3 (instead of 4).

Based on these assumptions and using a two-sided α level of 0.05, the sample size to achieve 85% power was estimated at 160 participants (80 per group) in the AChR+ population. Under the assumption that up to 25 participants meeting the study eligibility criteria will be AChR- (MuSK+ or LRP4+), the total study sample size will be approximately 185 participants. This sample size also provides approximately 80% power for an analysis of the difference between the placebo and satralizumab groups in the proportion of MG-ADL responders in the mITT and AChR+ population. This power calculation assumes a 50% response rate in the placebo group and a 75% response rate in the satralizumab group.

3. ANALYSIS SETS

The following populations are defined (Table 3):

Table 3 Analysis Sets

Population	Definition
Intent to treat (ITT)	All randomized participants. This excludes adolescents joining the study after the last adult participant is randomized.

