4.2.3.4 Imputation Due to Intercurrent Events

In the following we describe missingness and data imputation due to IECs. A detailed statistical justification for this imputation strategy can be found in Wolbers M et al. (2021).

- 1. For each participant the time of the first ICE is determined using the ICE data set. For each efficacy score a data set is created where all subsequent data to the first ICE is removed. If a participant has multiple ICEs between which normal dosing of study drug is attained all the data are nevertheless removed in a first step, i.e., data that would be dealt under treatment policy is still removed in this step. This ensures that the imputation model is fitted on data that is completely unaffected by ICEs.
- 2. A mixed model repeated measures (MMRM) model is fitted as an imputation model to address all the missingness due to ICEs. The MMRM is modeling change from baseline of the efficacy score (separate MMRMs will be fitted for each score) and has the following covariates: treatment group, visit, treatment group x visit, baseline stratification factors (background therapy, auto-antibody type [where this applies], region), baseline efficacy score and baseline efficacy score x visit. ("x" refers to complete interactions). The MMRM will use an unstructured covariance overall, in case of convergence issues the covariance structure will be simplified to compound symmetry. The resulting model will serve as a model for all imputations of longitudinal data in the next step.

3. The MMRM model implies a multivariate normal imputation distribution conditional on baseline covariates and conditional on observed longitudinal data that is not affected by an ICE. The implied conditional mean of this normal distribution is used to impute missing data. Participants with an ICE but subsequent data available which falls under treatment policy will use the observed data and will not be imputed. Participants on the satralizumab arm with missing data due to an ICE in category SDCR will be imputed using the imputation model and their treatment group covariate will be artificially set to placebo (copy reference imputation), this way their data are imputed as if they had not had a benefit from the treatment after the ICE. This imputation procedure will result in a complete data set for each efficacy score. All the efficacy analyses will be conducted on the completed data sets.

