AChR = acetylcholine receptor; AChR+ = AChR-antibody seropositive (participants/population); gMG = generalized Myasthenia Gravis; LRP4 = low-density lipoprotein receptor-related protein 4; MG-ADL = Myasthenia Gravis Activities of Daily Living; ; MGC = Myasthenia Gravis Composite; MG-QoL = Myasthenia Gravis Quality of Life; MuSK = muscle-specific kinase; NSDCR = not study drug or condition related; OP = overall population; QMG = Quantitative Myasthenia Gravis score; QoL = quality of life; SDCR = study drug or condition related; Exacerbation = increase of non-ocular MG-ADL item by at least two points from baseline or achieving non-ocular item value of 3 when baseline was below 3.

4.3.2 Secondary Endpoints Under the Primary (Continuous) Estimand Framework

Secondary endpoints falling under the primary estimand framework (Table 6) will be analyzed the same way as the primary endpoint. The ANCOVA model will be analyzed by adjusting for the baseline value of the corresponding score, i.e., QMG change from baseline to 24 weeks will be adjusted for baseline QMG (instead of baseline MG-ADL).

The estimands for the secondary endpoints will be derived on the imputed data set of the primary estimand if the corresponding endpoint is solely based on the raw score.

4.3.3 Secondary Endpoints Under the Responder Estimand

To analyze secondary endpoints under the responder estimand framework (Table 6) each participant will have to be labelled as a responder or non-responder. This is done using the complete data set from the Imputation procedure and by applying the definition of the secondary endpoints. For a rationale on those responder definitions refer to the Study Protocol sections on MG-ADL, QMG and MGC responder definitions, which employ minimum clinically important difference derived in the relevant clinical literature. According to ICE specification of the responder estimand, participants that received rescue therapy will be imputed as non-responders (composite strategy) irrespective of the actual score in the completed data set.

A Cochran-Mantel-Haenszel test over the treatment groups stratifying for baseline stratification factors is the treatment effect estimator for the responder estimand. The estimate is the difference in proportion at Week 24.

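### Death is filled by copy reference and is not made a failure, so a participant who dies unrescued after improving can be counted as an MG-ADL responder with duration running to Week 24

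*SAP*

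**What the plan says.** SAP 4.2.1.2 recognises three intercurrent events: withdrawal from study treatment, rescue therapy, and interruption for infection. Death is not an event of its own. It is one of the withdrawal causes always classed as study drug or condition related: "SDCR: Adverse Event (AE), death, lack of efficacy".

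Table 5 gives that class the treatment-policy strategy, described as follows: "In the treatment policy strategy, the occurrence of SDCR ICE is ignored and measurements of the variable of interest are used as such". If later data are missing or partial, "then data are used as available and the remainder is imputed using copy reference". SAP 4.2.3.4 gives the mechanics. A satralizumab participant's treatment covariate is switched to placebo in the imputation model, and "The implied conditional mean of this normal distribution is used to impute missing data". The mean is conditional on baseline covariates and on the participant's own data from before the event.

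All efficacy analyses use the completed data sets. On labelling participants as responders or non-responders, SAP 4.3.3 states: "This is done using the complete data set from the Imputation procedure". Rescue therapy is the only event that forces non-response (SAP 4.3.1.1, 4.3.3). Under SAP 4.3.4 the duration count ends at Week 24, when the 2-point reduction is lost, or at rescue. No efficacy section treats death separately; it otherwise appears only as a safety summary in SAP 4.5.2.

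**The concern.** Treatment policy means using what was measured after the event. After death nothing can be measured, so the label does not describe what is done. For a death the plan estimates a score under continued survival on placebo.

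For a continuous score this is a debatable but stated assumption. For a binary or duration endpoint it gives a result few readers would accept. A participant who is rescued and recovers is a non-responder, while one who improves and then dies without rescue can be a responder with benefit credited to Week 24. Protocol 3.4.7.4 makes rescue a non-response because it is a significant event in its own right, and the same reasoning applies to death.

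Protocol 6.4.5 also promised a supplementary responder estimand with a composite strategy for this class of withdrawal. That analysis would have covered death, but the SAP does not contain it.

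**Working it through.** **Inputs** (SAP 2.2 unless noted): placebo improvement 2.3, satralizumab improvement 4.3, SD 3.97, two-sided alpha 0.05, power 85%, withdrawal 10%, 80 per arm, responder rates 50% and 75%. MG-ADL runs from 0 to 24 (SAP 4.2.1). The documents give no number of deaths, no baseline mean and no between-visit correlation; values used for the last two are assumptions.

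**The plan's own sample size.** Per arm, 2 × (1.960 + 1.036)² × 3.97² / 2.0² = 70.75, rounded up to 71; 71/0.9 gives 79 per arm, 158 in total. With the t distribution the figure is 71.7, rounded up to 72, and 72/0.9 = 80 per arm. The stated 160 is reproduced.

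**What a death is imputed as.** The planning text reads: "The assumed change from baseline to Week 24 in the placebo group is 2.3 points". Suppose the placebo mean is also 2.3 at the last visit seen, with equal SDs and no other covariates. Let x be the last observed improvement and ρ its correlation with Week 24. Then:

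imputed improvement = 2.3 + ρ × (x − 2.3)

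| ρ (assumed) | x = 0 | x = 2 | x = 4.3 | x needed to reach 2 points |
|---|---|---|---|---|
| 0.3 | 1.61 | 2.21 | 2.90 | 1.30 |
| 0.5 | 1.15 | 2.15 | 3.30 | 1.70 |
| 0.7 | 0.69 | 2.09 | 3.70 | 1.87 |
| 0.9 | 0.23 | 2.03 | 4.10 | 1.97 |

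The last column is 2.3 − 0.3/ρ. A participant last seen at an average satralizumab improvement (4.3), an average placebo improvement (2.3, imputed at 2.3) or exactly 2 is a responder throughout. One last seen unchanged is a non-responder whenever 2.3 × (1 − ρ) < 2, that is, ρ above 0.3/2.3 = 0.13. A conditional mean is imputed rather than a random draw, so an average-course death is always classed as a response, although the plan expects only 50% of placebo participants to respond.

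**Size on the responder endpoint.** Per reclassified death, 1/80 = 1.25 percentage points. In the satralizumab arm that is 60/80 = 75.0% to 59/80 = 73.75%, against a planned difference of 75 − 50 = 25 points.

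**Duration, by example.** Take a first 2-point reduction at Week 8 and a death after the Week 12 visit. The count can run to 24 − 8 = 16 weeks; ended at the last visit alive, it is 12 − 8 = 4. Whether it does reach Week 24 depends on the imputed values at Weeks 16, 20 and 24, and the documents state a placebo mean only for Week 24.

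**Minimal symptom expression.** Entry requires a screening MG-ADL of at least 5, and 5 − 2.3 = 2.7 is not 0 or 1. An average-course death would not qualify, so the rule matters here mainly for consistency.

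**Size on the continuous primary, per satralizumab death, depending on the value substituted:**
- no improvement instead of 2.3: 2.3/80 = 0.029 points, or 1.4% of the planned 2.0;
- worst score 24, assumed baseline 9: (24 − 9 + 2.3)/80 = 0.216, or 10.8%; the range is 0.266 to 0.141 for baselines 5 to 15.

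**The case against.** A reader might infer that every death enters the primary analysis as an improvement and that the error favours the arm with more deaths. The documents do not support this. The imputed value depends on the participant's own course. On the planning figures, an average placebo death is imputed near its own arm's mean and is neutral. An average satralizumab death is pulled from 4.3 toward 2.3, which lowers the treatment difference by up to 2.0/80 = 0.025. The rule favours an arm with deaths only by comparison with an analysis that scores death worse, and the size of that comparison is set by the score chosen (1.4% or about 11% of the planned effect per death). Table 4 also states the continued-on-placebo assumption openly.

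A reader might also picture fatal myasthenic crises being scored as successes. Protocol 1.1 gives no crisis mortality. Protocol 3.1.5 counts crisis among the exacerbations requiring rescue, and a participant rescued before dying is already a non-responder whose duration count has stopped. A death before any post-baseline MG-ADL falls outside the mITT population.

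The primary endpoint has partial cover as well. The tipping-point analysis in SAP 4.2.4.3 replaces values after satralizumab discontinuation with the last value plus an increasing penalty.

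All of this stands, and it confines the problem to the derived endpoints. It does not answer the remaining case: an unrescued death in a participant who had been improving. No rule in SAP 4.3 handles that case, and the tipping-point analysis reaches neither the placebo arm nor the secondary endpoints.

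**Conclusion.** The point holds for the binary and duration endpoints. As written, the SAP counts an unrescued death after an average or better course as an MG-ADL response and can let the duration count run to Week 24. Each such death is worth 1.25 percentage points in an arm of 80. This rests on the plan's assumed 2.3-point placebo improvement and on the simplified imputation formula above. The same rule governs the QMG and MGC responder endpoints, but the documents give no planned placebo change for those scores, so no figure can be put on them.

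The overall effect depends on the number of deaths, which may be zero. The responder and minimal-symptom endpoints are labelled supportive in Table 6, and neither they nor duration appear in the hierarchy of SAP 4.3.7, so no confirmatory claim turns on them. The documents do not support a finding of bias in the primary analysis. Putting a worst score into the main continuous analysis would be a trade-off, not a correction: a single unrelated placebo death scored 24 could move the difference by up to 0.27 points in satralizumab's favour (baseline 5).

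**What to change.** In SAP Table 5, 4.3.1.1, 4.3.3 and 4.3.4, separate death from the other withdrawal causes and treat it as composite for the binary and duration endpoints:

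- non-responder on MG-ADL, QMG and MGC;
- not minimal symptom expression;
- duration ends at the last visit alive.

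Leave the main continuous analysis unchanged. Add one named sensitivity analysis that gives deaths in both arms an unfavourable value, run once with no improvement and once with the worst score, so that the reader sees how far the choice matters.

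This takes a few lines of SAP text and needs no new data. It should be settled before unblinding, so that the rule cannot depend on which arm the deaths fall in. The downside is a slightly less favourable result on these endpoints for an arm with deaths.

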## 3.1.5 Unscheduled Visits and Rescue Therapy

Unscheduled visits can be performed at the discretion of the treating neurologist.

If a suspected gMG exacerbation occurs during the study, the participant should return to the study site and undergo the following evaluations before or immediately after any administration of the rescue therapy: MG-ADL, QMG, Myasthenia Gravis Composite

(MGC), and Myasthenia Gravis Quality of Life 15 Scale (revised) (MG-QOL 15r). Additional assessments, such as hematology, chemistry, and urinalysis, will be performed if an infection or a metabolic disturbance is suspected to be contributing to the clinical presentation necessitating the unscheduled visit.

MG exacerbation requiring rescue therapy is defined as one of the following:

- MG crisis (Sanders et al. 2016)
- Substantial symptomatic worsening that requires immediate therapy
- Health in jeopardy if rescue therapy is not given, as determined by the treating physician.

Rescue therapy includes IVIg and PE with or without high -dose corticosteroids as outlined in Section 4.3.3. The choice of rescue therapy will be determined by the investigator on the basis of his or her overall clinical assessment.

Study drug administration will be continued as scheduled, concurrently with rescue therapy, unless the investigator considers it necessary to interrupt or discontinue study treatment (see Section 5.1.4). Patients who receive PE as rescue therapy will receive loading doses of study drug as soon as possible post -PE. Site staff should consult the Medical Monitor as to how to schedule dosing in such circumstances.

Patients who receive rescue therapy during the DB period may receive OLE satralizumab after completion of the DB period.

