4.2.4.1 Impact of Rescue Therapy

To assess the impact of rescue therapy in AChR+ participants all values after the administration of rescue therapy are replaced by the worst possible MG-ADL assessment that a particular participant has had prior to receiving rescue therapy. This

imputation overwrites the estimand specified imputation strategy. The impact will be estimated using an MMRM.

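### Keeping one efficacy record per scheduled visit drops most unscheduled MG-ADL records, so the exacerbation proportion can be under-counted unless its item-level source is named

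*SAP*

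**What the plan says.** **Mapping.** SAP Section 4.2.1.2, after Table 5, has three sentences on visit mapping. The first reads "For the efficacy analysis data entries will be mapped to the closest visit available". The second bars mapping between the double-blind and OLE periods. The third, on duplicates, reads "If two data entries are mapped to the same visit, then the one closer to it and later will be used". None exempts unscheduled records or gives the planned assessment priority.

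**Collection.** Protocol Section 3.1.5: "If a suspected gMG exacerbation occurs during the study, the participant should return to the study site and undergo the following evaluations". The list is MG-ADL, QMG, MGC and MG-QOL 15r, taken before or immediately after rescue. The Appendix 1 schedule also marks MG-ADL at re-loading and end-of-treatment visits, so those records compete for the same slots.

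**Endpoint.** SAP Table 6 lists the proportion with at least one exacerbation as supportive in AChR+ and OP and exploratory in LRP4 & MuSK, among the responder rows. Its footnote defines exacerbation as "increase of non-ocular MG-ADL item by at least two points from baseline or achieving non-ocular item value of 3", the latter where baseline was below 3.

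**Data source.** Section 4.3.3 says of responder labelling: "This is done using the complete data set from the Imputation procedure and by applying the definition of the secondary endpoints". Section 4.3.1.1 uses the primary estimand's imputed data for endpoints under other estimands. Section 4.2.3.4 builds one completed data set per efficacy score and runs every efficacy analysis on these.

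**Related analyses.** Section 4.4.2.1 dates events, including time to exacerbation, by when they actually first occur. The rescue sensitivity analysis in Section 4.2.4.1 substitutes "the worst possible MG-ADL assessment that a particular participant has had prior to receiving rescue therapy".

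**The concern.** The unscheduled visit exists to document a suspected exacerbation. The mapping rule sets its record against a planned visit that by design lies near the nominal day, so the planned record usually wins. If the endpoint is read from what remains, a patient who worsened and was treated between visits counts as having no exacerbation unless the worsening also shows at a planned visit.

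Three things are at stake:

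- The exacerbation proportion could be too low. If exacerbations follow the planning assumption for rescue (20% placebo, 10% satralizumab), more would be lost on placebo and the difference would shrink.
- The proportion and the time-to-event analysis could report different numbers of patients with the same event.
- The worst pre-rescue MG-ADL could be missed if it is taken from mapped data.

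A separate matter is that *closer* and *later* are joined without an order, so two programmers could keep different records for the same visit.

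**Working it through.** **1. The plan's own figure.** Inputs from SAP Section 2.2: difference 4.3 − 2.3 = 2.0, SD 3.97, two-sided α 0.05, power 85%, withdrawal 10%. n per arm = 2(1.960 + 1.036)²(3.97/2.0)², which rounds up to 71. 71/0.90 gives 79 per arm, 158 in total. The t-test version gives 72, then 72/0.90 = 80 per arm, 160 in total. The stated 160 reproduces, and the mapping rule does not change it.

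**2. The rule by hand.** Appendix 1 places the visits on Days 1, 15, 29, 57, 85, 113, 141 and 169, with windows of ±3 days (Weeks 2 and 4) and ±7 days (Week 8 onward).

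- Planned visit on Day 57, unscheduled visit on Day 66. 66 − 57 = 9 and 85 − 66 = 19, so both records map to Week 8. The planned record is 0 days from target and the unscheduled one 9, so on *closer* the unscheduled record is dropped.
- Unscheduled visit on Day 167, Week 24 visit on Day 173. The distances from Day 169 are 2 and 4. *Closer* picks the unscheduled record and *later* picks the planned one.

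**3. How often records are dropped.** Simulation of 400,000 patients per scenario. Assumptions not in the documents: one unscheduled MG-ADL on a uniformly random day before the actual Week 24 visit, all planned visits attended, and the visit-timing spreads shown. Entries nearest Day 1 count as not kept.

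| Planned-visit timing | Kept: closest wins, later breaks ties | Kept: later wins | Kept: both required | *Closer* and *later* disagree | Week 24 displaced (closest wins) |
|---|---|---|---|---|---|
| On nominal day | 0% | 44.0% | 0% | 44.0% | 0% |
| SD 1 day | 4.8% | 44.1% | 1.7% | 43.1% | 0.27% |
| SD 2 days | 10.7% | 44.1% | 4.2% | 43.4% | 0.72% |
| SD 3 days | 16.1% | 44.1% | 6.7% | 43.6% | 1.20% |
| Uniform over window | 23.3% | 44.1% | 9.7% | 44.5% | 2.01% |

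So 77–100% of unscheduled records are dropped when closest wins, and about 56% on the most lenient reading.

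**4. Which data the endpoint uses.** Sections 4.2.3.4, 4.3.1.1 and 4.3.3, with the placement in Table 6, send the exacerbation proportion to the completed data sets. Those hold one score per scale and visit. The Table 6 footnote needs individual non-ocular items. So the endpoint either comes from mapped records, without most unscheduled ones, or cannot be computed from the named source.

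**5. What planned visits can see.** MG-ADL recall is 7 days (Protocol Section 4.5.8.2). Seven post-baseline visits × 7 days = 49 days, and 49/168 = 29%. This is coverage of calendar time, not a share of events.

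**6. Effect on the primary result.** Take the rescue rates as a proxy for patients with one unscheduled visit, the highest displacement in the table (about 2%), and an assumed displaced score 10 points worse. Affected: 80 × 0.20 × 0.02 = 0.32 placebo and 80 × 0.10 × 0.02 = 0.16 satralizumab patients. Shift in the difference: 10 × 0.02 × (0.20 − 0.10) = 0.02 points, which widens it slightly. Power at 72 per arm moves from 85.6% to 86.3%. With a 3-point worse score the shift is 0.006 points.

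**The case against.** **A dropped record is not a lost event.** An item-level definition cannot be applied to a total-score data set, so a programmer may well go back to the unmapped items. Protocol Section 6.4.4 keeps this proportion outside the estimand framework and Section 6.4.5 gives it separate consideration. This stands as far as it goes: the item-level source is unspecified, and under-counting is possible but not shown. It does not settle the matter, because SAP Section 1 gives the SAP precedence over the protocol for filings, and the SAP's own text points to the completed data.

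**Other parts are already safe.** Time to exacerbation uses actual times. Rescue use has its own variable and a dated intercurrent-event data set (Sections 4.3.5 and 4.2.2.1), so the confirmatory rescue endpoint does not depend on mapping. Both points stand. Rescue does not fill the gap, however. The SAP defines exacerbation by MG-ADL items alone, so a rescued patient could be counted as having none, although Protocol Section 6.4.5 treats rescue as always following an exacerbation.

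**The rescue sensitivity analysis may be unaffected.** Section 4.2.4.1 does not restrict itself to mapped visits, and the unscheduled assessment may come just after rescue. This stands, so the effect there is only conditional.

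**The tie rule has a coherent reading.** Closest first, later as tie-break, is workable, so the sentence is not a contradiction. But it is not what the SAP states, and the two criteria disagree for about 43–45% of simulated entries.

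**The stakes are modest.** The endpoint is supportive and outside the testing hierarchy, and if losses follow the rescue pattern they would shrink the difference rather than create one. This stands.

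**Conclusion.** The concern holds in a limited form. Followed as written, the SAP computes the exacerbation proportion on data that omit most unscheduled MG-ADL records, and it names a data set that does not carry the items the definition needs. The proportion can be under-counted and can disagree with the time-to-exacerbation analysis. The worst pre-rescue MG-ADL is exposed in the same way if it is taken from mapped data. The 56–100% range for dropped records rests on the assumed timing in the simulation.

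A reader might infer three stronger conclusions that the documents do not support:

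- *Most exacerbations would be lost.* The documents give no exacerbation rate or duration, and no share of events still visible at the next planned visit. The loss of events cannot be derived.
- *The 71% of days outside recall windows measures missed events.* It would do so only if worsening lay wholly between windows. Rescue rates are also not exacerbation rates, since the protocol's criteria for rescue differ from the SAP's item-based definition.
- *The Week 24 primary value is compromised.* For patients entering the OLE, displacement is 0–2% per unscheduled entry when closest wins and 0% on the other two readings, worth at most about 0.02 points. A patient who does not enter the OLE could have a record after an early Week 24 visit that is both closer and later. That case is outside the simulation, and no rate is given for it.

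The sample size of 160 and the primary conclusion are not in question.

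**What to change.** Two changes to the SAP, before unblinding:

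1. State that exacerbation yes/no and the worst pre-rescue MG-ADL are derived from all observed double-blind item-level MG-ADL records (scheduled, unscheduled, re-loading and end-of-treatment) before visit mapping. This matches the actual-time rule in Section 4.4.2.1. Add an exception for these derivations where Sections 4.2.3.4, 4.3.1.1 and 4.3.3 refer to the completed data.
2. In Section 4.2.1.2, state that by-visit analyses use the planned-visit record when it exists, otherwise the record closest to the target day, with the later one only to break a tie.

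The cost is a short SAP edit and one derivation. The data are already collected, and neither the sample size nor the testing hierarchy changes.
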